## **Statement of Compliance**

(1) [The trial will be conducted in accordance with International Conference on Harmonization Good Clinical Practice (ICH GCP), applicable United States (US) Code of Federal Regulations (CFR), and the <specify NIH Institute or Center (IC) > Terms and Conditions of Award. The Principal Investigator will assure that no deviation from, or changes to the protocol will take place without prior agreement from the Investigational New Drug (IND) or Investigational Device Exemption (IDE) sponsor, funding agency and documented approval from the Institutional Review Board (IRB), except where necessary to eliminate an immediate hazard(s) to the trial participants. All personnel involved in the conduct of this study have completed Human Subjects Protection and ICH GCP Training.

The protocol, informed consent form(s), recruitment materials, and all participant materials will be submitted to the IRB for review and approval. Approval of both the protocol and the consent form must be obtained before any participant is enrolled. Any amendment to the protocol will require review and approval by the IRB before the changes are implemented to the study. All changes to the consent form will be IRB approved; a determination will be made regarding whether a new consent needs to be obtained from participants who provided consent, using a previously approved consent form.]

## List of Abbreviations

AE	Adverse Event
CFR	Code of Federal Regulations
CRF	Case Report Form
CTSC	Clinical Translational Science Center
DSMB	Data Safety Monitoring Board
DSMP	Data Safety Monitoring Plan
FDA	Food and Drug Administration
GCP	Good Clinical Practice
HIPAA	Health Insurance Portability and Accountability Act of 1996
HRBFA	Human Research Billing Analysis Form
HUD	Humanitarian Use Device
ICF	Informed Consent Form
IDE	Investigational Device Exemption
IND	Investigational New Drug
IRB	Institutional Review Board
PHI	Protected Health Information
PI	Principal Investigator
SAE	Serious Adverse Event
SUSAR	Suspected Unexpected Serious Adverse Reaction
UIRTSO	Unanticipated Problem Involving Risks to Subjects or Others
WCM	Weill Cornell Medicine

## 1. Protocol Summary

Full Title:	Evaluation of Ability to Detect Bowel Gas during Laparoscopic Right Colectomy with Intracorporeal Anastomosis
Short Title:	Perf-Alert™ Pilot Study
Clinical Phase:	I
Principal Investigator:	[name] [name]
Study Description:	
Undetected bowel perforation is a rare but dangerous complication of laparoscopic surgery. If the injury is not detected and treated at the time of the surgical procedure, the patient can suffer severe complications, including septic shock and eventually death. Our goal is to test a novel device that can detect bowel gas leakage from perforation and alert the surgeon during the operation by evaluating the gases present in the insufflated abdomen during surgery. This study will determine the ability of the device to be attached to a standard trocar during the operation and periodically draw small samples or aliquots of gas from the abdomen to evaluate the gas and accurately detect gaseous content from the bowel. Before the device can be used to detect bowel perforations, we must first ensure that it can accurately detect bowel gas in an insufflated abdomen.

Sample Size:	N= 20
Enrollment:	This study will enroll 20 subjects and screen up to 50 subjects.
Study Population:	Participants of any gender over the age of 18 undergoing laparoscopic right colectomy with intracorporeal anastomosis procedures for regular care of their medical condition.
Enrollment Period:	12 months
Study Design:	Prospective pilot, interventional, single-center, single arm, open-label, investigator-initiated study of 20 subjects in 2 cohorts: Cohort 1- 10 subjects and Cohort 2- 10 subjects, to determine device ability to detect bowel gas during laparoscopic right hemicolectomy with intracorporeal anastomosis.
Description of Sites/	Single site study
Facilities Enrolling	Weill Cornell Medicine
Participants:	20
Study Duration:	14 months from initiation to study completion (12 months accrual, 2 months data analyses and presentation).
Participant Duration:	4-6 weeks. From enrollment and consent during preoperative clinic visit (Visit 1) and during surgery (Visit 2). Data will be gathered preoperatively and intraoperatively during the laparoscopic right colectomy.
Study Agent/Device Name	Perf-Alert™, Sentire Medical Systems, Inc., USA
Intervention Description:	The anesthesia and the laparoscopic surgical procedure will be performed as per standard of care. Perf-Alert™ was developed by Sentire Medical Systems, Inc., USA. The Perf-Alert™ prototype

*consists of a 15" x 13" x 7" unit containing gas sensors and valves, a small box containing a one-way, ultra-low pressure pump, user controls (buttons), and software algorithms, which control the operation of the device. It is used in conjunction with a single-use, disposable kit consisting of sterile tubing and filters used for sample collection and transport. The sensing unit will be connected via a sterile tube/filter set to any trocar port in use during the procedure. At specific time points during the procedure, a one-way valve will be opened, and the unit's pump turned on and withdrawing a small aliquot of gas from the abdominal cavity to the sensing unit. The system's architecture is configured such that sample collection, transport, analysis, and feedback occur in a single step such that sample collection and sensor feedback occur in real-time. A standard laptop running an analytical software program is connected to the unit to record and log sensor readings.*

**Primary Objective:**

*The primary objective of this study is to test the Perf-Alert™ device's ability to detect, in humans, bowel gas leakage [Hydrogen (H2) and Methane (CH4)] into an insufflated abdomen during laparoscopic right colectomy with intracorporeal anastomosis*

**Secondary Objectives:**

*The secondary objective of this study is to determine response time of the Perf-Alert™ device.*

**Exploratory Objectives:** N/A**Primary Endpoints:**

Presence of Hydrogen (H2) and Methane (CH4) gas measured in ppm or mg/L (parts per million or milligrams per liter (mg/L) at 8 time points during the surgery:

- 1) Initiation of surgery/laparoscopy start Insufflation
- 2) Abdominal exploration
- 3) Completion of colon mobilization
- 4) Colon transection
- 5) At Colotomy
- 6) At Enterotomy
- 7) Anastomosis completion
- 8) End of surgery- after re-insufflation before closure

All data to be analyzed will be gathered during a single surgical procedure

**Secondary Endpoints:**

The response time of the Perf-Alert™ device measured in seconds from obtaining the sample (from opening the valve to obtain sample) to first detecting a gas presence at the device electronic sensors.

**Covariates:**

Demographics  
Preoperative Diagnosis  
Existing Medical Conditions  
Statin drugs in the last 3 months  
Antibiotics in the last 3 months  
Intra-abdominal pressure  
Anesthetic gases  
Total CO2 volume  
Intraoperative complications

**1.1 Schema**

Prior to Enrollment

Total N: Obtain informed consent. Screen potential participants by inclusion and exclusion criteria; obtain history, vital stats (age, gender, height, weight, BMI) document.

Arm 1  
20 participants

Surgery Initiation Time Point

Connect Perf Alert™ to Operative Trocar Port  
Sterile tube/filter assembly to be opened in sterile field and affixed to accessible trocar port via standard leur connection ensuring air-tight seal. Surgeon or OR nurse will hand the other end of the tube to the Perf-Alert™ operator for connection.

Post Insufflation Time Point

Post insufflation but prior to initiation of surgical procedure, initiate **Sample Collection** as follows: 1. Open valve of trocar port to allow abdominal gas to pass through. 2. Open valve at Perf-Alert™ and initiate sample collection by turning on pump – let run for 60 seconds. 3. Close valve of trocar to stop the flow of gas from the abdomen.

Time points For Sample Collection

- 1) Initiation of surgery/laparoscopy start Insufflation
- 2) Abdominal exploration
- 3) Completion of colon mobilization
- 4) Colon transection
- 5) At Colotomy
- 6) At Enterotomy
- 7) Anastomosis completion
- 8) End of surgery- after re-insufflation before closure

End of Surgery Time Point

Prior to conclusion of surgery and removal of trocars, repeat Sample Collection procedure.

Post Operative

**Final Assessments**  
Statistical analysis to be performed on gas concentration measurements collected

## 1.2 Study Objectives and End Points

### 1.2.1 Primary Objectives

To test the Perf-Alert™ device's ability to detect, in humans, bowel gas leakage [Hydrogen (H2) and Methane (CH4)] into an insufflated abdomen during laparoscopic right large intestinal surgery with intracorporeal anastomosis.

### 1.2.2 Secondary Objectives

*The secondary objective of this study is to determine response time of the Perf-Alert™ device.*

### 1.2.3 Exploratory Objectives

N/A

### 1.2.4 Primary Endpoints

The primary end points are the presence of Hydrogen (H2) and Methane (CH4) gas measured in ppm or mg/L (parts per million or milligrams per liter (mg/L) at 8 time points during the surgery.

- 1) Initiation of surgery/laparoscopy start Insufflation
- 2) Abdominal exploration
- 3) Completion of colon mobilization
- 4) Colon transection
- 5) At Colotomy
- 6) At Enterotomy
- 7) Anastomosis completion
- 8) End of surgery- after re-insufflation before closure

Initiation of surgery and end of surgery. All data to be analyzed will be gathered during a single surgical procedure.

### 1.2.5 Secondary Endpoints

The response time of the Perf-Alert™ device measured in seconds from obtaining the sample (from opening the valve to obtain sample) to first detecting a gas presence at the device electronic sensors.

### 1.2.6 Covariates:

Demographics  
Preoperative Diagnosis  
Existing Medical Conditions  
Statin drugs in the last 3 months  
Antibiotics in the last 3 months  
Intra-abdominal pressure

Anesthetic gases  
Total CO2 volume  
Intraoperative complications

## 2. Background

### 2.1 Disease

Undetected intraoperative bowel injuries are rare but devastating complications of laparoscopic surgery. Intraoperative small and large intestinal injuries have been reported in the range of 0.1-9.2%, and 1.3-4.8% are diagnosed after surgery [1-3]. Multiple risk factors are described in the literature to play a role in the iatrogenic bowel injuries such as lysis of adhesions, history of previous abdominal surgery, electrocautery, utilization of grasping forceps or scissor, obesity, bowel obstruction, and restricted visual field [1-7]. Further, laparoscopic procedures such as large bowel resections with anastomosis can often develop leaks leading to similar complications including severe morbidity and mortality. The leak test is one method of testing for anastomotic leak after completion of bowel anastomosis, although some studies show it has not significantly decreased the anastomotic leak occurrence [8]. Another intervention to prevent the occurrence of an anastomotic leak or to decrease the severity of the leak after the occurrence is diverting stoma creation, with conflicting reports on its role in leak prevention [9]. If the injury is not detected and treated at the time of the surgical procedure, the patient can suffer severe complications including septic shock and eventually death [1, 7-12].

A novel alternative method for early detection of intraoperative bowel injuries may help to avoid or decrease some of the most dreadful postoperative complications such as peritonitis, septic shock, and eventually death. Bowel gases Hydrogen (H2) and Methane (CH4) are only two of the gases produced in the large intestine as a by-product result of bacterial fermentation [12-13]. When the bowel is injured or intentionally opened during surgery, these gases escape into the abdominal cavity and could be useful for early detection of bowel injury. Sentire Medical Systems, USA has developed a novel device that may be able to detect these gases during surgery. Unpublished data from preclinical studies show that the device sensors were able to detect small quantities of hydrogen and methane gases within 30 seconds of analysis [12]. The first human trial with 8 patients undergoing Roux-en-y gastric bypass reported that hydrogen gas was detected by the Sentire device in real-time during surgery, and suggested that the device could be used for the detection of iatrogenic intraoperative bowel injuries [12].

This study aims to test the Perf-AlertTM device's ability to detect, in humans, bowel gas leakage [Hydrogen (H2) and Methane (CH4)] into an insufflated abdomen during laparoscopic right colon surgery with intracorporeal anastomosis.

### 2.2 Investigational Agent/Device, or Surgical Treatment/Method

Our goal is to test a novel device that can detect bowel gas leakage from perforation and alert the surgeon during the operation by evaluating the gases present in the insufflated abdomen during surgery. During laparoscopic surgery, CO2 is inserted into the abdominal cavity in order to perform the operation. This is a dynamic process as insufflation is constant during the entire procedure to maintain constant pressure and compensate for any small leaks due to the insertion and retrieval of instruments.

This study will determine the ability of a novel device to be attached to a standard trocar during the operation and periodically draw a small amount of gas from the abdomen to evaluate the gas and

accurately detect gaseous content from the bowel. Before the device can be used to detect bowel perforations, first we must ensure that it can accurately detect bowel gas in an insufflated abdomen.

The Investigational device, Perf-Alert™, consists of a 15" x 13" x 7" unit containing gas sensors and valves, a small box containing a one way, ultra-low pressure pump, user controls (buttons), and software algorithms, which control the operation of the device ( Image1). It is used in conjunction with a single-use, disposable kit consisting of sterile tubing and filters used for sample collection and transport (Image 2). The sensing unit will be connected via a sterile tube/filter set to any trocar port in use during the procedure. At specific time points during the procedure, a one-way valve will be opened and the unit's pump turned on pulling small aliquots of gas from the abdominal cavity to the sensing unit. The system's architecture is configured such that sample collection, transport, analysis, and feedback occur in a single step such that sample collection and sensor feedback occur in real-time. A standard laptop running an analytical software program is connected to the unit to record and log sensor readings. No changes to the device are anticipated during the course of the study.

Image1. Investigational device, Perf-Alert™

Image 2. A single use, disposable kit consisting of sterile tubing and filters

## 2.3 Rationale

Undetected bowel perforation is a rare but dangerous complication of laparoscopic surgery. If the injury is not detected and treated at the time of the surgical procedure, the patient can suffer severe morbidity, including septic shock and eventually death. Inadvertent and undetected bowel perforations have occurred during laparoscopic surgeries of all types: cholecystectomy, hernia repair, hysterectomy, oophorectomy, etc. Further, laparoscopic procedures involving the bowel, such as bariatric (foregut) and colorectal (bowel resections and anastomosis), can often develop leaks leading to similar complications, including severe morbidity and mortality [1, 7-9]. This research is important to the colorectal surgery field as it may provide an alternative for early detection of bowel injury or anastomosis leak during the intraoperative time, and thus avoid or decrease some of the most dreadful postoperative complications such as peritonitis, septic shock, and eventually death.

## 2.4 Risk/Benefit Assessment

### 2.4.1 Known Potential Risks

No changes in the care or treatment of the patients will be made as a result of this study, it is only intended to be observational, and therefore, minimal risk is anticipated. The technology being studied will not come into direct contact with the patient. A sterile tubing will be connected to the trocar in the patient during the operation. As sterile tubing is routinely connected to trocars, there is little to no physical risk to the patient. The same type of tubing and setup will be used for measurements as the one used for the insufflation of CO2.

Another potential physical risk is the time under anesthesia. The additional amount of time that the patient will be under anesthesia due to the collection of the gas samples will be under 5 minutes, mitigating any increased risk to the patients due to a long duration under anesthesia.

Another potential physical risk is the need to ex-sufflate and re-insufflate the abdomen prior to the final gas sample collection. Ex-sufflation and re-insufflation occur routinely during laparoscopic surgery due to instrument exchange, and since there will be no instruments in the patient during this ex-sufflation/re-insufflation, the risk to the patient will be no higher than the risk during the regular surgical procedure. The surgeon and study personnel will be responsible for triggering the device to sample the intra-abdominal gas at the predefined time points, they will not have direct contact with any bodily fluids or gases. Therefore, we do not anticipate any significant risks or exposure risks to the patients or study personnel.

Finally, a previous clinical study involving the roux-en-y bariatric procedure was conducted with no adverse patient events [11]. Information on this study is available at Clinicaltrials.gov (<https://clinicaltrials.gov/ct2/show/NCT02679118?term=Sentire&cond=Bowel+Perforation&cntry=US&rank=1>)

Another potential risk related to this research is the loss of privacy. However, all the necessary measures will be taken to protect the subject's privacy. The electronic data will be kept in password-protected computers and the paper data will be stored in a locked cabinet in the locked research office located at K802B.

#### **2.4.2 Known Potential Benefits**

There will not be any direct benefits to the participating subjects. This device is not intended to treat or to alter treatment, therefore we do not expect there to be any benefit to the participating subjects in this study.

We hope the information learned from this study will lead to the development of a solution that could minimize intraoperative bowel injury and would be of significant benefit to future patients and providers.

#### **2.4.3 Assessment of Potential Risks and Benefits**

Given the potential benefits offered by minimizing one of the most consequential and costly complications of laparoscopy, the potential risks of the study are minimal. Specifically, the device to be investigated will not come into contact with the patient at any time and is simply connected via a standard tube set to a trocar in use during the procedure. The tubing utilized is the same as that used to connect the insufflator to the trocar and standard in all laparoscopic procedures. Secondly, the surgeon will not alter the procedure in any way, with the exception of 60-90 second pauses at each time point during sample collection. The total additional anesthesia time required for each subject will be less than 5 minutes. We believe the benefits of this study overweight the risk.

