#### Design

Prospective pilot, single-center, single arm, open label, phase 1 investigator-initiated study to determine device ability to detect bowel gas during laparoscopic right colectomy with intracorporeal anastomosis using Perf-Alert™ gas detection system on 20 subjects into 2 Cohorts.

**Cohort 1:** 10 subjects with measurement of bowel gas at 8 predetermined time points during right laparoscopic colectomy as follow:

- 1) Initiation of surgery/laparoscopy start Insufflation
- 2) Abdominal exploration
- 3) Completion of colon mobilization
- 4) Colon transection
- 5) At Colotomy
- 6) At Enterotomy
- 7) Anastomosis completion
- 8) End of surgery- after re-insufflation before closure

**Cohort 2:** 10 subjects with continuous monitoring of bowel gases through the surgery. The level of H2 and CH4 gases will be noted at the 8 predetermined time points during the continuous monitoring as well.

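### The stated added anesthesia time of under 5 minutes conflicts with the plan's own sampling pauses, which total 8-12 minutes in Cohort 1 if each pause adds operating time

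*Combined protocol and SAP*

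**What the plan says.** Section 2.4.3 describes the study's effect on the operation in two adjacent sentences. The first says that "the surgeon will not alter the procedure in any way, with the exception of 60-90 second pauses at each time point during sample collection". The second reads: "The total additional anesthesia time required for each subject will be less than 5 minutes".

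Section 2.4.1 names time under anesthesia as a physical risk and answers it with the same limit: "The additional amount of time that the patient will be under anesthesia due to the collection of the gas samples will be under 5 minutes". It then raises a further step: "Another potential physical risk is the need to ex-sufflate and re-insufflate the abdomen prior to the final gas sample collection". No duration is given for that step, and section 2.4.3 does not list it with the pauses.

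The number of samples comes from section 3.1. Cohort 1 is "10 subjects with measurement of bowel gas at 8 predetermined time points during right laparoscopic colectomy". Cohort 2 is "10 subjects with continuous monitoring of bowel gases through the surgery", with gas levels noted at the same 8 points. Sections 1.1, 1.2.4, 6.1.2 and 12.1 also list 8 points.

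Two other places bear on the pause length. The schema in section 1.1 tells the operator to start the pump and "let run for 60 seconds". Section 13.1 gives 90 seconds for drawing one sample.

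**The concern.** A pause of 60-90 seconds at each of 8 time points does not fit inside 5 minutes, so the two sentences in section 2.4.3 appear to contradict each other.

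The limit is a number the plan relies on. It is the only reason section 2.4.1 offers for regarding the anesthesia-time risk as mitigated, and section 2.4.3 repeats it just before concluding that benefits outweigh risks. Section 2.4.2 says: "There will not be any direct benefits to the participating subjects". The IRB is therefore weighing added anesthesia time against no personal gain, using a figure lower than the one the plan's own procedure produces.

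**Working it through.** **Inputs**

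- Pause per time point: 60-90 s (section 2.4.3). The two ends match the 60 s pump run in section 1.1 and the 90 s draw in section 13.1.
- Time points in Cohort 1: 8 (section 3.1).
- Stated limit: under 5 min = 300 s per subject (sections 2.4.1 and 2.4.3).
- Ex-sufflation and re-insufflation before the last sample: duration not given, so left out of the sums.
- Assumption: each pause adds its full length to the operation.

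**Can the plan's figure be reproduced?** Added time = number of pauses x pause length.

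| Pauses that add time | At 60 s (min) | At 90 s (min) |
|---|---|---|
| 2 | 2.0 | 3.0 |
| 3 | 3.0 | 4.5 |
| 4 | 4.0 | 6.0 |
| 5 | 5.0 | 7.5 |
| 6 | 6.0 | 9.0 |
| 7 | 7.0 | 10.5 |
| 8 | 8.0 | 12.0 |

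It cannot be reproduced with 8 pauses. A total under 5 minutes across the whole 60-90 s range needs at most 3 pauses. Four pauses fit only if each is shorter than 300/4 = 75 s.

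**Size of the gap with 8 pauses**

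- At 60 s: 8 x 60 = 480 s = 8 min. Ratio 480/300 = 1.6; excess 480 - 300 = 180 s = 3 min.
- At 90 s: 8 x 90 = 720 s = 12 min. Ratio 720/300 = 2.4; excess 720 - 300 = 420 s = 7 min.

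**What would have to be true for the limit to hold**

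- Share of pause time adding nothing: more than 180/480 = 37.5% at 60 s, or more than 420/720 = 58.3% at 90 s.
- In whole pauses: 4 at 60 s take 240 s and fit, but 5 take 300 s and do not fall under the limit. Three at 90 s take 270 s and fit. So at least 4 of 8 (60 s) or 5 of 8 (90 s) must cost no time.
- On average, each of the 8 pauses may add less than 300/8 = 37.5 s.

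**Cohort 2.** The plan does not say whether the surgeon pauses. The added time is 0 min if not, and 8-12 min if the same pauses are held.

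**Possible origin (inference only).** The endpoint list in section 1.2.4 is followed by a fragment naming only the start and end of surgery. Two samples would give 2-3 minutes, which fits the stated limit, so the figure may have been carried over from a design with fewer samples. Nothing in the documents confirms this.

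**The case against.** The strongest reply is that pause length and added anesthesia time are different quantities, and they conflict only if every pause prolongs the operation in full. Some overlap is plausible. The first sample is taken after insufflation and before the surgical procedure starts. The last is taken after re-insufflation, and section 2.4.1 says no instruments are in the patient during that step. A coordinator runs the device outside the sterile field (section 7.1), and the insufflator replaces the withdrawn gas as it is drawn (sections 13 and 13.1), so no separate recovery time is implied.

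This shows that the additivity assumption is needed, but it does not rescue the figure. If the first and last samples cost nothing, 6 pauses remain, or 6-9 minutes. Section 2.4.3 itself presents the pauses as the one departure from the usual procedure, which implies that surgery stops, and no section describes sampling alongside surgical work.

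It is also fair to say that the effect is modest. The possible excess is 3-7 minutes in 10 subjects, and the documents give neither an operating time nor a risk per added minute, so no change of risk category can be shown. The inputs are in plain view, so an attentive IRB member could do the sum. The ex-sufflation step is already disclosed as a risk in section 2.4.1, and its time cannot be quantified. These points limit how serious the matter is; they do not reconcile the figures.

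**Conclusion.** The concern holds. As written, the limit of under 5 minutes is inconsistent with the pauses the plan prescribes: 8-12 minutes per Cohort 1 subject, before any study-driven time for ex-sufflation and re-insufflation. The result rests on each pause adding operating time, which section 2.4.3 implies and nothing in the plan contradicts.

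The conclusion is narrow. It does not say that 8-12 minutes is unsafe or that the minimal-risk judgement fails. The other supports for that judgement (no direct device contact and no energy delivered, section 13.1.1; CO2 replacement, section 13) are untouched, and so is the analysis of the primary endpoint. It should be corrected because it misstates a burden on subjects that the IRB is asked to weigh.

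**What to change.** In sections 2.4.1 and 2.4.3, do one of the following:

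- Replace the limit with about 8-12 minutes for Cohort 1, plus an estimate for ex-sufflation and re-insufflation before the last sample. This suits the case where the surgeon does stop at every time point.
- Keep the limit, but name the time points that need no added pause and show that the rest stay below 5 minutes. That allows at most 4 pauses of 60 s or 3 of 90 s.

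In either case, state whether Cohort 2 pauses, and list ex-sufflation and re-insufflation in section 2.4.3 as an exception alongside the pauses. Optionally, record a pause end time next to the collection time already in the section 6.1.2 table, so that the actual added time can be reported.

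The cost is small: text edits, with IRB review of the larger figure if the first option is taken. The optional recording adds one field to the collection form. The consent form was not available for this review; if it repeats the figure, it needs the same edit. Sample size and analysis do not change.
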